6.2.2 TIMING OF DOSE ADMINISTRATION

Trial treatment should be administered on day 1 of each treatment cycle after all procedures/assessments have been completed as detailed on the trial flow chart (Section 7.0). Trial treatment may be administered up to 3 days before or after the scheduled day 1 of each cycle due to administrative reasons. Interruptions from the treatment plan for > 3 days and up to 3 weeks may be allowed, but require consultation between the principal investigator and treating investigator, and written documentation of the collaborative decision on subject management.

Pembrolizumab will be administered as a 30 minute (+/- 5 minute) IV infusion every 21 days, unless a treatment-limiting toxicity (TLT), as defined in Section 6.2.1.2 and as outlined in **Table 5**, has occurred. In this case, provided that the patient has sufficiently recovered, pembrolizumab will be restarted as a 30 minute (+/- 5 minute) IV infusion every 21 days. All trial treatments will be administered on an outpatient basis.

In the setting where a subject assessment is consistent with progressive disease (PD) at the 3 month disease response assessment, study drug may be continued until next disease response assessment provided the subjects' clinical condition is stable. If progressive

disease is noted on imaging and patient is clinically stable or improved, repeat imaging should be obtained 4-6 weeks later. **This exception pertains to B cell lymphoma patients only.**

If a subject is noted to have progression of disease at a time point beyond the 3 month disease response assessment, a repeat assessment may not be performed and the subject should not receive further treatment with the study medication.

Subjects may only receive study treatment if the following criteria are met:

- Absence of signs and symptoms (including worsening of laboratory values indicative of disease progression)
- No decline in ECOG performance status
- Absence of rapid disease progression

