6.8 SUBJECT WITHDRAWAL/DISCONTINUATION CRITERIA

Subjects may withdraw consent at any time for any reason or be removed from the trial at the discretion of the investigator should any untoward effect occur. In addition, a subject may be withdrawn by the investigator or the sponsor if enrollment into the trial is inappropriate, the trial plan is violated, or for administrative and/or other safety reasons.

A subject must be discontinued from the trial for any of the following reasons:

- The subject or legal representative (such as a parent or legal guardian) withdraws consent.

A subject must be discontinued from treatment (but may continue to be monitored in the trial) for any of the following reasons:

- The subject or legal representative withdraws consent for treatment
- Disease progression occurs
- Unacceptable AEs develop as described in Tables 5 and 6, and Sections 6.6.1.1 and 6.6.1.2
- Intercurrent illness develops that prevents further administration of pembrolizumab
- Investigator's decision
- The subject becomes pregnant
- The subject is non-compliant with the treatment or trial requirements

- The subject is lost to follow-up
- Administrative reasons

The end of treatment and follow-up visit procedures are listed in Section 7.0 (Trial flow chart) and Section 8.1.5 (Visit Requirements). After the end of treatment, each subject will be followed for 30 days for adverse event monitoring (serious adverse events will be collected for 90 days after the end of treatment). Subjects who discontinue for reasons other than progressive disease will have post-treatment follow-up for disease status until disease progression, initiating a non-study cancer treatment, withdrawing consent or becoming lost to follow-up. After documented disease progression or the start of new anti-cancer therapy, each subject will be followed by telephone for overall survival until death, withdrawal of consent, or the end of the study, whichever occurs first.

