8.1.2.6.3 DISEASE ASSESSMENT OF IMMUNOTHERAPEUTIC AGENTS

Note - this section pertains to subjects with B cell lymphomas only. Immunotherapeutic agents such as pembrolizumab may produce anti-tumor effects by potentiating endogenous cancer-specific immune responses, which may be functionally anergic. The response patterns seen with such an approach may extend beyond the typical time course of responses seen with cytotoxic agents, and can manifest a clinical response after an initial increase in tumor burden or even the appearance of new lesions.

Standard response assessment criteria may not provide a complete response assessment of immunotherapeutic agents such as pembrolizumab. Therefore in the setting where a subject assessment shows PD, study drug may be continued until next disease response assessment provided that the subjects' clinical condition is stable. Repeat scans after suspected "pseudoprogression" should be obtained in 4-6 weeks; if scans confirm progression, pembrolizumab will be discontinued. If progression is not confirmed on repeat imaging, the patient may continue on therapy. However, imaging should occur at any time where there is clinical suspicion of progression.

Note - with the next disease response assessment if the disease is clinically stable or clinically improved, an exception may be considered to continue treatment upon consultation with the principal investigator.

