8.1.2.6.9 DISEASE PROGRESSION ASSESSMENTS

A subject with B cell lymphoma ONLY with evidence of progressive disease documented at the week 12 assessment may continue trial treatment until next response assessment provided the subjects' clinical condition is stable. However, imaging should occur at any time where there is clinical suspicion of progression. Repeat scans after suspected "pseudoprogression" should be obtained in 4-6 weeks; if scans confirm progression, pembrolizumab will be discontinued. If progression is not confirmed on repeat imaging, the patient may continue on therapy. Subjects may only receive treatment if the following criteria are met:

- Absence of signs and symptoms (including worsening of laboratory values) indicating disease progression
- No decline in ECOG performance status
- Absence of rapid progression of disease
- Absence of progressive tumor at critical anatomical sites (e.g. cord compression) requiring urgent alternative medical intervention

After the first disease response assessment, it is at the discretion of the investigator to keep a clinically stable subject on trial treatment or to stop trial treatment until a repeat assessment is performed. Subjects that are deemed clinically unstable after first disease response assessment at week 13 should not continue trial treatment and must be discontinued from the trial.

For subjects who have stable disease, partial response, or complete response following the first disease response assessment (at week 13), disease assessments and imaging should continue per the regular frequency every 12 weeks as outlined in the trial flow chart.

For subjects noted to have progression of disease at a time point beyond the week 13 initial disease response assessment, it is at the discretion of the investigator to keep a

clinically stable subject on trial treatment or to stop trial treatment until a repeat assessment is performed.

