12.6.6 DEFINITIVE PROGRESSION

NHL, HL, MDS, and AML response and progression data will be subjected to IRC review. The subject should continue on study pending confirmation of progression by the IRC.

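### After progression beyond the week-13 assessment, 6.2.2 ends study drug while 8.1.2.6.9 leaves it to the investigator, and the DOR definitions do not say whether first or confirmed progression counts

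*Combined protocol and SAP*

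**What the plan says.** **Treatment after progression**

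- Section 6.2.2 allows continuation after progressive disease at the 3-month assessment, for B cell lymphoma only. For "progression of disease at a time point beyond the 3 month disease response assessment" it says that "a repeat assessment may not be performed and the subject should not receive further treatment with the study medication".
- Section 8.1.2.6.9 opens with a rule for B cell lymphoma only. Its last paragraph refers to subjects without naming a disease. For progression "beyond the week 13 initial disease response assessment, it is at the discretion of the investigator" whether a stable patient stays on drug or pauses it until a further assessment has been made.
- Section 8.1.2.6.3, limited to B cell lymphoma, says that "in the setting where a subject assessment shows PD, study drug may be continued until next disease response assessment", provided the subject is clinically stable. It does not restrict this to the first assessment.
- Section 6.8 states: "A subject must be discontinued from treatment (but may continue to be monitored in the trial) for any of the following reasons". Disease progression is on the list that follows.

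**Staying on study, and who confirms progression**

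- Section 2.1 removes from the study any patient with biopsy-proven progression.
- Section 12.6.6 sends response and progression data for all four disease groups to an IRC and adds: "The subject should continue on study pending confirmation of progression by the IRC".
- Sections 8.1.2.6.2, 8.1.2.6.4 and 8.1.2.6.5 say that there is no central radiology or pathology review.

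**DOR**

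- Section 3.2 ends DOR at subsequent progression or relapse.
- Section 5.4 ends it at documentation of progression and refers back to 3.2 for the definition, which 3.2 does not contain.
- Section 9.2.4.2.2 specifies a Kaplan-Meier curve and nothing about event dates.

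**The concern.** An investigator who finds progression at, say, week 25 in a stable lymphoma patient can cite one section for stopping drug and another for continuing it. Exposure after progression would then depend on which section was read. The protocol itself raises a GVHD concern with PD-1 blockade in this setting (section 4.3), so that exposure also bears on the safety data collected.

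DOR has a related but separate gap. Where a repeat assessment is done, progression has two candidate dates, and the plan does not choose between them. Response is first assessed on schedule at week 13, so a responder's progression would normally be found later, in the period where the two treatment rules disagree.

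**Working it through.** The plan states no figure on this point, so the check compares the text and then does interval arithmetic.

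**Step 1. Do the two rules cover the same situation?** Section 6.2.2 speaks of the 3-month assessment and 8.1.2.6.9 of week 13. The flow chart (7.2) puts the first on-treatment imaging and marrow at week 13, day 1 of cycle 5. Section 8.1.2.6.10 lists the 3-month sample in its text and week 13 in its Table 9. They are the same visit, so both rules govern progression found after it.

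**Step 2. Can both be followed?**

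| Section | Diseases | Study drug after later progression | Repeat assessment |
|---|---|---|---|
| 6.2.2 | Not restricted for later progression | None | May not be performed |
| 8.1.2.6.9, last paragraph | Lymphoma; AML/MDS unclear | Investigator decides | Foreseen |
| 8.1.2.6.3 | Lymphoma only | May continue if stable | At 4-6 weeks |
| 6.8 | All | Must stop | Not addressed |

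For lymphoma, the first two rows contradict each other on any reading. The last two rows do not settle it: 8.1.2.6.3 leans towards continuation and 6.8 towards stopping.

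**Step 3. Is the DOR end date fixed elsewhere?** In 3.2, the phrase about first documentation is attached to ORR, not DOR. Section 8.1.6.4.1 uses confirmed progression, but only to start survival follow-up. Table 12 in 9.1.2 adds only that non-responders are excluded. First versus confirmed is left unstated.

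**Step 4. Size.** Inputs: repeat scan at 4-6 weeks (8.1.2.6.3, 8.1.2.6.9); scheduled assessments every 12 weeks (8.1.2.6.6); dosing every 21 days (6.2.1.1).

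Shift in DOR = date of confirming assessment − date on which progression was first documented:

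- repeat scan: 4 × 7 = 28 days to 6 × 7 = 42 days;
- next scheduled assessment: 12 × 7 = 84 days;
- first documentation used under either rule: 0 days.

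Further doses, assuming progression is found on day 1 of a cycle (day 0 below) and counting doses before the confirming assessment:

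- drug stopped at once (6.2.2), or held until the repeat (an option in 8.1.2.6.9): 0;
- drug continued to a repeat at day 28-42: days 0 and 21, so 2 doses (1 if the day-0 dose is not given);
- drug continued to day 84: days 0, 21, 42 and 63, so 4 doses (3 if the day-0 dose is not given).

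The range is 0 to 4 doses.

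**The case against.** The best defence is that the treatment conflict does not itself move the DOR date. The response criteria in the appendix define progression or relapse by findings, with no confirmation step, and 5.4 ends DOR at documentation of progression. An analyst can therefore use the first documented date whether or not drug continues. This stands: the DOR effect is conditional, and it comes from the missing first-versus-confirmed rule. A reader might infer that the treatment conflict alone leaves DOR undetermined, or that investigators who continue drug will report longer responses. The documents support neither, because nothing says the later date would be used.

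A second defence is that the prohibition on repeat assessment in 6.2.2 could be read as saying only that one might not be done. Even so, its bar on further treatment still contradicts the discretion in 8.1.2.6.9.

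Third, a reader might infer that 12.6.6 clashes with the mandatory stop in 6.8. It does not: 12.6.6 keeps the subject on study, and 6.8 expressly allows monitoring to continue after treatment stops. The real conflicts of 12.6.6 are with 2.1, which removes patients with biopsy-proven progression, and with the sections that rule out central review.

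Fourth, the affected group is limited. The continuation provisions are written for lymphoma, and 6.2.2 and 8.1.2.6.9 require no symptoms or signs of progression, no ECOG decline and no rapid progression. This also stands, and it is why the point should not be read as covering every enrolled patient.

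**Conclusion.** The contradiction between 6.2.2 and 8.1.2.6.9 is real and should be removed. It is certain for B cell lymphoma and uncertain for AML and MDS. Nothing here says which treatment rule is right; the documents contradict themselves and must be reconciled. The position of the IRC is a second, separate inconsistency.

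The DOR consequence is smaller and conditional. If the confirming assessment sets the date, an affected response is 4-6 weeks longer, or up to 12 weeks if the next scheduled assessment is used. If first documentation is used, there is no difference. Further doses range from 0 to 4. These figures assume the stated 12-week and 21-day spacing and progression found on a dosing day. Four doses is the extreme case, since the sections on suspected pseudoprogression call for a repeat at 4-6 weeks.

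A reader might infer that the primary conclusion is at risk. It is not: the DLT thresholds (5 of 12, 14 of 26) and the sample size do not depend on this rule. DOR is a secondary endpoint, summarised among responders in a pilot of 12 to 26 patients.

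**What to change.** 1. Reconcile 2.1, 6.2.2, 6.8, 8.1.2.6.3, 8.1.2.6.9 and 12.6.6 into one rule chosen by the sponsor. It should state which diseases it covers, keep stopping treatment distinct from leaving the study, and say whether an IRC exists.
2. Add to 9.2.4.2.2: *DOR ends on the date progression or relapse is first documented, whether or not treatment continues or a repeat assessment is done, unless a repeat assessment shows that it was not progression.*

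The sentence works under either treatment rule. If no repeat is allowed, the first documented date stands. If a repeat is done and confirms progression, the date does not move. A sentence that depended on confirmation would give no end date where no repeat is done.

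The cost is protocol wording and one sentence in the analysis plan. DOR may be slightly shorter than under dating at confirmation.

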6.2.3 EXTENT OF TRIAL TREATMENT

All subjects who experience a partial response or have stable disease may remain on treatment for up to 2 years, or until progression.

Subjects who achieve a complete response may choose to discontinue pembrolizumab therapy. However, they will not be eligible for re-treatment on this study should the disease recur before or after the planned 2 year treatment period.

6.2.4 TRIAL BLINDING/MASKING

This is an open-label trial. The investigator and subject will be aware of the study treatment administered.

6.3 RANDOMIZATION OR TREATMENT ALLOCATION

Subjects participating in this trial will be allocated by non-random assignment.

6.4 STRATIFICATION

No stratification based on age, sex or other characteristics will be used in this trial.

6.5 CONCOMITANT MEDICATIONS AND VACCINES.

Medications or vaccinations specifically prohibited in the exclusion criteria are not allowed. If there is a clinical indication for any medication or vaccination specifically prohibited during the trial, discontinuation from trial therapy or vaccination may be required. The treating investigator should discuss any questions regarding this with the principal investigator and drug manufacturer, Merck (as appropriate). The final decision on any supportive therapy or vaccination rests with the investigator and/or the subject's primary physician. However, the decision to continue the subject on trial therapy or

vaccination schedule requires the mutual agreement of the investigator, the principal investigator and the subject.

6.5.1 ACCEPTABLE CONCOMITANT MEDICATIONS

All treatments that the investigator considers necessary for a subject's welfare may be administered at the discretion of the investigator in keeping with the community standards of medical care. All concomitant medication will be recorded on the case report form (CRF) including all prescription, over-the-counter (OTC), herbal supplements, and IV medications and fluids. If changes occur during the trial period, documentation of drug dosage, frequency, route, and date may also be included on the CRF. Subject may remain on anti-coagulation therapy as long as the PT or PTT is within therapeutic range of the intended use of anticoagulants

All concomitant medications received within 28 days before the first dose of trial treatment and 30 days after the last dose of trial treatment should be recorded. Concomitant medications administered after 30 days after the last dose of trial treatment should be recorded for SAEs and ECIs as defined in Section 8.2.

6.5.2 PROHIBITED CONCOMITANT MEDICATIONS AND TREATMENTS

- Anti-neoplastic systemic chemotherapy or biological therapy
- GM-CSF
- Immunotherapy not specified in this protocol
- Investigational agents other than pembrolizumab
- Radiation therapy (Radiation therapy to a symptomatic solitary lesion may be allowed after consultation with the investigator.
- Live vaccines within 30 days prior to the first dose of pembrolizumab and through the duration of the study. Examples include, but are not limited to: measles, mumps, rubella, chicken pox, yellow fever, rabies, BCG, oral typhoid, and intranasal influenza vaccines (e.g. Flu-Mist[®]). Seasonal influenza vaccines for injection are generally acceptable.
- Immunosuppressive medications including, but not limited to, systemic corticosteroids (>10 mg/day prednisone or equivalent), methotrexate, azathioprine, and tumor necrosis factor alpha (TNF- α) blockers. Use of immunosuppressive medications for the management of investigational product-related AEs and in subjects with contrast allergies is permitted. The use of physiologic steroid replacement may be approved after consultation with the investigator, study PI, and sponsor. In addition, use of inhaled and intranasal corticosteroids is permitted.

- Other medications as outlined in the exclusion criteria (Section 6.1.3).

6.6 RESCUE MEDICATIONS AND SUPPORTIVE CARE

6.6.1 SUPPORTIVE CARE GUIDELINES

Subjects should receive appropriate supportive care measures as deemed necessary by the treating physician, including but not limited to the items outlined below:

- Diarrhea: Subjects should be carefully monitored for signs and symptoms of enterocolitis (such as diarrhea, abdominal pain, blood or mucus in stool, with or without fever) and bowel perforation (such as peritoneal signs and ileus). Diarrhea in this particular patient population may be due either to acute GVHD or to classical pembrolizumab-induced enterocolitis, and the differentiation between the two may be difficult or impossible. In symptomatic subjects, infectious etiologies should be evaluated, and if symptoms are persistent and/or severe, endoscopic evaluation should be performed.
- In subjects with severe enterocolitis (grade 3 or 4) caused by acute GVHD or classical pembrolizumab-associated enterocolitis, pembrolizumab will be permanently discontinued, and treatment with systemic corticosteroids should be initiated at a dose of 1-2 mg/kg/day of prednisone or equivalent. When symptoms improve to \leq grade 1, a corticosteroid taper should be started and continued for > 1 month.
- In subjects with moderate enterocolitis (grade 2) caused by acute GVHD or classical pembrolizumab-associated enterocolitis, pembrolizumab will be withheld and corticosteroids should be initiated at a dose of 1 mg/kg/day of prednisone or equivalent. When symptoms improve to \leq grade 1, a corticosteroid taper should be started and continued for > 1 month. Pembrolizumab may be re-started at 200 mg IV every 21 days, as outlined in Section 6.2.1.2.
- All subjects who experience diarrhea should be advised to drink liberal quantities of clear fluids. If sufficient oral fluid intake is not feasible, fluid and electrolyte repletion (IV) is appropriate. Other treatments, including loperamide, oral non-absorbable corticosteroids and octreotide may be administered according to institutional guidelines for the treatment of acute GVHD.
- GVHD: Subjects should be carefully monitored for signs and symptoms of GVHD (including diarrhea, transaminitis, rash). These symptoms will be treated aggressively with topical and/or systemic steroids and additional immunosuppressants per institutional guidelines.
- Nausea/vomiting: These symptoms should be treated aggressively, and consideration should be given in subsequent cycles to the administration of prophylactic anti-emetics according to institutional practice.

- Antibiotics: Antibiotics, either prophylactic or therapeutic, are allowed as considered appropriate by the treating physician. **Appropriate antibiotics (i.e. PCP prophylaxis) should be initiated for patients who are on longer courses of corticosteroids.**
- Immune-related adverse events: Please see Table 5 above and separate guidance document regarding diagnosis and treatment of adverse events of a potential immunologic etiology.
- Infusion reactions: Acute infusion reactions (which include cytokine release syndrome, angioedema, or anaphylaxis) are unique from allergic/hypersensitive reactions, although some of the manifestations are common to both. Signs and symptoms usually develop during or shortly after pembrolizumab infusion and generally resolve completely within 24 hours of completion of infusion. Signs/symptoms may include: allergic reaction/hypersensitivity (including fever), arthralgia, bronchospasm, cough, dizziness, dyspnea, fatigue, headache, hypertension, hypotension, tachycardia, rigors or chills, myalgia, nausea, vomiting, pruritus, rash or urticaria, and tumor pain. See **Table 6** below for management guidelines for pembrolizumab-associated infusion reactions.
- Respiratory/Pulmonary adverse events: Investigators should maintain a high index of suspicion for pneumonitis and initiate treatment with corticosteroids in a timely manner. Additional supportive care guidance for pneumonitis can be found in Section 6.6.1.2.

Table 6. Infusion reaction treatment guidelines

NCI CTCAE Grade	Treatment	Premedication at subsequent dosing
Grade 1 Mild reaction; infusion interruption and intervention not indicated.	Increase monitoring of vital signs as medically indicated until the subject is deemed medically stable in the opinion of the investigator.	None
Grade 2 Requires infusion interruption but responds promptly to treatment (e.g., antihistamines, NSAIDS, narcotics, IV fluids); prophylactic medications indicated for	Stop Infusion. Additional appropriate medical therapy may include but is not limited to: IV fluids Antihistamines NSAIDS Acetaminophen Narcotics	Subject may be pre-medicated 1.5h (± 30 minutes) prior to infusion of pembrolizumab with: Diphenhydramine 50 mg PO (or equivalent

NCI CTCAE Grade	Treatment	Premedication at subsequent dosing

≤ 24 hrs
	
Increase monitoring of vital signs as medically indicated until the subject is deemed medically stable in the opinion of the investigator.
 
If symptoms resolve within one hour of stopping drug infusion, the infusion may be restarted at 50% of the original infusion rate (e.g. from 100 mL/hr to 50 mL/hr). Otherwise dosing will be held until symptoms resolve and the subject should be pre-medicated for the next scheduled dose.
 
Subjects who develop Grade 2 toxicity despite adequate premedication should be permanently discontinued from further trial treatment administration.
	
antihistamine dose).
 
Acetaminophen 500-1000 mg PO (or equivalent dose of antipyretic).

Grade 3 or 4
 
Grade 3: Prolonged (not rapidly responsive to symptomatic medication and/or brief interruption of infusion); recurrence of symptoms following initial improvement; hospitalization indicated for other clinical sequelae (e.g., renal impairment, pulmonary infiltrates)
	
Stop Infusion.
 
Additional appropriate medical therapy may include but is not limited to:
 
 IV fluids Antihistamines NSAIDS Acetaminophen Narcotics Oxygen Corticosteroids Epinephrine 
Increase monitoring of vital
	
No subsequent dosing

NCI CTCAE Grade	Treatment	Premedication at subsequent dosing
Grade 4: Life-threatening; pressor or ventilatory support indicated	
signs as medically indicated until the subject is deemed medically stable in the opinion of the investigator.
 
Hospitalization may be indicated.
 
Subject is permanently discontinued from further trial treatment administration.
	

Appropriate resuscitation equipment should be available in the room and a physician readily available during the period of drug administration.
 
For further information, please refer to the Common Terminology Criteria for Adverse Events v4.0 (CTCAE) at http://ctep.cancer.gov
		

6.6.1.1 SUPPORTIVE CARE GUIDELINES FOR ADVERSE EVENTS OF CLINICAL INTEREST WITH AN IMMUNE ETIOLOGY (IRAES) AND EVENTS OF CLINICAL INTEREST (ECI)

Immune-related adverse events (irAE)

irAEs are defined as an adverse event associated with pembrolizumab exposure and mediated through an immune mechanism. irAEs may be predicted based on the nature of the known mechanism of action of pembrolizumab, as well as experience with other immunotherapies with a similar mechanism of action. Special attention should be paid to AEs that are suggestive of potential irAEs. An irAE can occur shortly after the first dose, or several months after the final dose of pembrolizumab. If an irAE is suspected, effort should be made to rule out other potential etiologic causes prior to labeling an AE as an irAE. Information on how to identify and evaluate irAEs is included in the event of clinical interest and immune-related adverse event guidance document located in the administrative binder.

Events of clinical interest (ECI)

ECIs are non-serious and serious AEs that may or may not be irAEs. ECIs must be reported to Merck within 24 hours regardless of attribution to pembrolizumab.

Information on how to identify and report ECIs can be referenced in Section 8.2.3.2.

